5.2 Discussion of Trial Design

This is a Phase II single-arm trial to determine the efficacy and safety of avelumab in subjects with metastatic MCC. There is currently no approved treatment for advanced or metastatic MCC; thus a single-arm trial is appropriate. Furthermore, as there is no solid evidence of therapeutic efficacy in any second-line chemotherapy regimen, no concomitant therapy is justified. Planned interim analyses during the trial ensure a minimum number of subjects are exposed to the study drug in the case of insufficient clinical activity. The dosing regimen is based upon the current ongoing Phase I trials. The primary endpoint will be the confirmed BOR according to RECIST 1.1. Responses provide a direct measure of antitumor activity in subjects treated with the study drug. The confirmed BOR will be used to determine the ORR, which is suitable for a single-arm Phase II trial. The response status at 6 and 12 months after start of treatment, duration of response, and PFS and OS times will also be determined and will serve to assess whether the ORR is associated with lasting clinical benefit. A within-subject comparison of PFS time on study versus TTP on prior treatment will also serve as a comparative evaluation of subjects' outcome under treatment with avelumab.

With regard to Part B, the benefit of avelumab in metastatic MCC as initial therapy is unknown; however, preliminary results from an ongoing Phase II study (Part A of this study) in second-line or greater metastatic disease has documented an ORR greater than a predefined futility rate (data not shown). Also, a similar mechanism of action (pembrolizumab, an anti-PD-1 antibody) has demonstrated a substantial ORR (71% in evaluable patients) in treatment naïve metastatic or

unresectable MCC (Nghiem 2016). Given the known clinical activity of avelumab in a variety of tumor types (refer to avelumab IB) and given the expression of PD-L1 with CD8 T cell presence in Merkel cell tumors (Afanasiev 2013) it is plausible that avelumab offers benefit. Further risk / benefit considerations are discussed in Section 3.6.

With regard to Part B, DRR is reasonable as a primary endpoint based on several factors. In a disease setting that is highly chemoresponsive but with short duration (NCCN 2016), DRR may describe response in a more clinically meaningful way compared with ORR. Adopting DRR of 6 months as a time-sensitive endpoint for the analysis of the Part B appears logical, especially since 6 months is viewed as a clinically relevant timepoint when considering response duration in metastatic MCC patients, given the fact that median survival in metastatic MCC is 9 months (Voog 1999) and that chemo-responses are noted as “not durable” by NCCN with median duration of response in Stage IV cited as 3 to 9 months (Iyer 2016, Satpute 2014, Tai 2000, Voog 1999, Sharma 1991). Also, the recent precedent of Imlygic regular approval by FDA based on a DRR endpoint suggests that DRR of 6 months is clinically meaningful (Imlygic SBA). In order to provide an estimation of the DRR, a total of 112 subjects will be enrolled (see Section 8.1).

5.2.1 Inclusion of Special Populations

Not applicable.

5.3 Selection of Trial Population

5.3.1 Inclusion Criteria

For inclusion in the trial, all of the following inclusion criteria must be fulfilled:

1. Signed written informed consent
2. Male or female subjects aged ≥ 18 years
3. Histologically proven MCC
 - a. Confirmation of the diagnosis by immunohistochemistry detection of CK20 (or other appropriate cytokeratin expression such as pancytokeratin, AE1/AE3, or Cam5.2; local laboratory testing) in the tumor cell is mandatory
 - b. Subjects must have metastatic disease; subjects with non-metastatic MCC that is only recurrent or unresectable are NOT eligible; for Part B, M1 status must be confirmed at entry
 - c. For Part A: Subjects must have received at least 1 line of chemotherapy for the treatment of metastatic MCC and must have progressed after the most recent line of chemotherapy that was administered. Subjects must have received at least one of the following chemotherapy regimens for treatment of metastatic MCC: Cyclophosphamide, topotecan, doxorubicine, epirubicin, vincristine, carboplatin, cisplatin, etoposide in combination with carboplatin or cisplatin

- d. For Part B: Subjects must not have received any prior systemic treatment for metastatic MCC. Prior chemotherapy treatment in the adjuvant setting (no clinically detectable disease; no metastatic disease) is allowable if the end of treatment occurred at least 6 months prior to study start
4. For Part A: Collection of biopsy material is required (fresh biopsy or recent biopsy [within 4 weeks prior to enrollment], for subjects unable to provide a fresh or recent biopsy, archival material is acceptable).

For Part B:

- 1) Priority: A recently obtained formalin-fixed, paraffin-embedded (FFPE) block containing tumor tissue (preferably within 6 months). If no tumor tissue is available, fresh biopsy will be required
 - 2) Priority: If the tumor containing FFPE tissue block cannot be provided in total, sections from this block should be provided that are freshly cut (within 1 week). Preferably, 25 slides should be provided; if not possible, a minimum of 10 slides in consultation with the Medical Monitor is required
5. ECOG PS of 0 to 1 at trial entry
 6. Estimated life expectancy of more than 12 weeks
 7. Disease must be measurable with at least 1 unidimensional measurable lesion by RECIST 1.1 (including skin lesions)
 8. Adequate hematological function defined by WBC count $\geq 3 \times 10^9/L$ with absolute neutrophil count (ANC) $\geq 1.5 \times 10^9/L$, lymphocyte count $\geq 0.5 \times 10^9/L$, platelet count $\geq 100 \times 10^9/L$, and hemoglobin ≥ 9 g/dL (may have been transfused)
 9. Adequate hepatic function defined by a total bilirubin level $\leq 1.5 \times$ the upper limit of normal (ULN) range and AST and ALT levels $\leq 2.5 \times$ ULN for all subjects
 10. Adequate renal function defined by an estimated creatinine clearance > 30 mL/min according to the Cockcroft-Gault formula or by 24 hour urine collection for creatinine clearance or according to local institutional standard method
 11. **Highly** effective contraception (that is, methods with a failure rate of less than 1% per year) for both male and female subjects if the risk of conception exists (Note: The effects of the study treatment on the developing human fetus are unknown; thus, women of childbearing potential and men must agree to use highly effective contraception, defined in [Appendix III](#) or as stipulated in national or local guidelines. **Highly** effective contraception must be used 28 days prior to first study treatment administration, for the duration of study treatment, and at least for 60 days after stopping study treatment. Should a woman become pregnant or suspect she is pregnant while she or her partner is participating in this study, the treating physician should be informed immediately.)

5.3.2 Exclusion Criteria

Subjects are not eligible for this trial if they fulfill any of the following exclusion criteria:

1. Participation in another interventional clinical trial within the past 30 days (participation in observational studies are permitted)
2. Concurrent treatment with a nonpermitted drug
3. Prior therapy with any antibody/drug targeting T-cell coregulatory proteins (immune checkpoints) such as anti-PD-1, anti-PD-L1, or anticytotoxic T-lymphocyte antigen-4 (CTLA-4) antibody; for Part B, the Investigator must consult with the Medical Monitor and consider other co-regulatory targets such as 4-1BB
4. Concurrent anticancer treatment (for example, cytoreductive therapy, radiotherapy [with the exception of palliative bone-directed radiotherapy, or radiotherapy administered on non-target superficial lesions], immune therapy, or cytokine therapy except for erythropoietin). Radiotherapy administered to superficial lesions is not allowed if such lesions are considered target lesions in the efficacy evaluation or may influence the efficacy evaluation of the investigational agent
5. Major surgery for any reason, except diagnostic biopsy, within 4 weeks and/or if the subject has not fully recovered from the surgery within 4 weeks
6. Concurrent systemic therapy with steroids or other immunosuppressive agents, or use of any investigational drug within 28 days before the start of trial treatment. Short-term administration of systemic steroids (that is, for allergic reactions or the management of irAEs) is allowed while on study. Also, subjects requiring hormone replacement with corticosteroids for adrenal insufficiency are eligible if the steroids are administered only for the purpose of hormonal replacement and at doses ≤ 10 mg or equivalent prednisone per day. Note: Subjects receiving bisphosphonate or denosumab are eligible
7. Subjects with active central nervous system (CNS) metastases are excluded. Subjects with a history of treated CNS metastases (by surgery or radiation therapy) are not eligible unless they have fully recovered from treatment, demonstrated no progression for at least 2 months, and do not require continued steroid therapy
8. For Part A: Previous malignant disease (other than MCC) within the last 5 years with the exception of basal or squamous cell carcinoma of the skin or cervical carcinoma in situ

For Part B: Previous malignant disease (other than MCC) within the last 5 years with the exception of basal or squamous cell carcinoma of the skin or carcinoma in situ (skin, bladder, cervical, colorectal, breast, or low grade prostatic intraepithelial neoplasia or Grade 1 prostate cancer)
9. Prior organ transplantation, including allogeneic stem-cell transplantation

10. For Part A, known history of testing positive for HIV or known acquired immunodeficiency syndrome (AIDS) or any positive test for hepatitis B virus (HBV) or hepatitis C virus (HCV) indicating acute or chronic infection. For Part B, known history of testing positive for HIV or known AIDS or HBV or HCV infection at screening (positive HBV surface antigen or HCV RNA if anti-HCV antibody screening test positive)
11. Active or history of any autoimmune disease (except for subjects with vitiligo) or immunodeficiencies that required treatment with systemic immunosuppressive drugs
12. Known severe hypersensitivity reactions to monoclonal antibodies (Grade ≥ 3 NCI-CTCAE v 4.0), any history of anaphylaxis, or uncontrolled asthma (that is, 3 or more features of partly controlled asthma)
13. Persisting toxicity related to prior therapy Grade > 1 NCI-CTCAE v 4.0; however, sensory neuropathy Grade ≤ 2 is acceptable
14. Pregnancy or lactation
15. Known alcohol or drug abuse
16. Clinically significant (that is, active) cardiovascular disease: cerebral vascular accident / stroke (< 6 months prior to enrollment), myocardial infarction (< 6 months prior to enrollment), unstable angina, congestive heart failure (New York Heart Association Classification Class $\geq II$), or serious cardiac arrhythmia requiring medication
17. All other significant diseases (for example, inflammatory bowel disease), which, in the opinion of the Investigator, might impair the subject's tolerance of trial treatment
18. Any psychiatric condition that would prohibit the understanding or rendering of informed consent
19. Legal incapacity or limited legal capacity
20. Nononcology vaccine therapies for prevention of infectious disease (for example, seasonal flu vaccine, human papilloma virus vaccine) within 4 weeks of study drug administration. Vaccination while on trial is also prohibited except for administration of inactivated vaccines (for example, inactivated seasonal influenza vaccine)

5.4 Criteria for Randomization/Initiation of Treatment with the Investigational Medicinal Product

The inclusion and exclusion criteria will be checked at the Screening visit. Eligible subjects will be enrolled before treatment start after verification of fulfilling all inclusion criteria without matching any exclusion criterion.

5.5 Criteria for Subject Withdrawal

5.5.1 Criteria for Withdrawal from Study Drug due to Therapeutic Failure

Subjects may continue avelumab treatment beyond radiological disease progression in the absence of significant clinical deterioration and, if in the opinion of the Investigator, the subject will benefit from continued treatment.

Before stopping the treatment with avelumab, progressive disease (PD) should be confirmed by imaging, preferably 6 weeks (but no later) after progression has been diagnosed according to RECIST 1.1.

If progression is based on the occurrence of a new lesion in an area not scanned at baseline, a further on-trial scan 6 weeks later should be performed. Treatment during the confirmation period should continue as scheduled, despite a first observation of progression (according to RECIST 1.1), until confirmation has been made, and further if there is no significant clinical deterioration defined as:

- there are no new symptoms or worsening of existing symptoms,
- there is no change in ECOG PS to ≥ 3 that lasts more than 14 days, or
- the Investigator does not consider it necessary to administer a salvage therapy.

If disease progression is due to brain metastasis, subjects may continue avelumab treatment after the local treatment of the brain lesions provided the above criteria are met in addition to the following and in consultation with the Medical Monitor:

- Brain metastases have been treated locally and are clinically stable for at least 2 weeks prior to re-initiation of treatment with avelumab
- There are no ongoing neurological symptoms that are related to the brain localization of the disease (sequelae that are a consequence of the treatment of the brain metastases are acceptable)
- Subjects must be either off steroids or on a stable or decreasing dose of ≤ 10 mg daily prednisone (or equivalent).

In addition, if disease progression is mainly due to a metastatic lesion (nodal or visceral) that in the opinion of the Investigator may be surgically removed or treated with palliative radiation therapy, subjects may continue avelumab treatment after the local treatment of such a lesion provided that:

- It has been at least 2 weeks (post minor surgery) or 4 weeks (post major surgery) and the subject has fully recovered from the surgery
- It has been at least 2 weeks since the subject's last dose of radiation therapy and any toxicity related to the radiation therapy is recovered to Grade < 2

The decision to continue treatment should be discussed with the Medical Monitor and documented in the trial records.

Subjects who experience significant clinical deterioration, as defined above, in the absence of confirmed PD should be discontinued from further treatment with avelumab.

The treatment with avelumab should be stopped immediately, if the subject does not tolerate avelumab anymore or if therapeutic failures occur, which requires urgent additional drug or results in clinical progression/deterioration.

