- therapeutic failure (subjects may stay on treatment beyond observation of progressive disease [PD] provided there is no significant clinical deterioration);
- unacceptable toxicity; or
- any criterion for withdrawal from the trial or the study drug is fulfilled.

Significant clinical deterioration is defined as

- new symptoms or worsening of symptoms that cannot be managed by optimal supportive care or disease localization that require immediate medical or surgical intervention (for example, lesion close to the spine), and/or
- change in Eastern Cooperative Oncology Group Performance Status (ECOG PS) to ≥ 3 that lasts more than 14 days.

Decisions regarding medical management of subjects will be made by the Investigator; however, the primary and secondary endpoint determinations will be according to tumor assessments performed by the IERC.

The date of the first observation of PD by RECIST 1.1 by the IERC will be used to determine the date of the PD as well as the duration of response in all subjects, including the subjects for which treatment was maintained beyond first determination of disease progression.

Adverse events will be assessed throughout the trial period and evaluated using the National Cancer Institute (NCI) Common Technology Criteria version 4.0 (CTCAE v 4.0).

Health-related quality of life will be assessed using a generic instrument (EuroQol EQ-5D [EQ-5D]), a cancer-specific instrument including a melanoma-specific module (Functional Assessment of Cancer Therapy – Melanoma [FACT-M]), and subject interviews (optional).

In Part A there will be 1 interim analysis for futility after 20 subjects have been enrolled and observed for at least

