5.1.1 Overall Design

In Part A, up to 84 subjects are planned to be enrolled and in Part B, up to 112 eligible subjects are planned to be enrolled. In both Part A and Part B, subjects will receive avelumab at a dose of 10 mg/kg once every 2 weeks. Tumor measurements (including the assessment of skin lesions by physical examination) to determine response will be performed every 6 weeks until 12 months

after the first study drug administration, then every 12 weeks thereafter and response to the treatment will be evaluated by RECIST 1.1. Treatment will continue until:

- therapeutic failure (subjects may stay on treatment beyond radiological disease progression provided there is no significant clinical deterioration, see Section 5.5.1),
- unacceptable toxicity, or
- any criterion for withdrawal from the trial or study drug is fulfilled (see Section 5.5).

For Part A: Subjects who have experienced a confirmed complete response (CR) should be treated for a minimum of 6 months and a maximum of 12 months after confirmation, at the discretion of the Investigator. If the Investigator believes that a subject may benefit from treatment beyond 12 months, it may be permissible after discussion with the sponsor. Part B: Subjects who have experienced a confirmed CR should be treated for a minimum of 12 months after confirmation, at the discretion of the Investigator. If the Investigator believes that a subject may benefit from treatment beyond 12 months, it may be permissible after discussion with the sponsor. For both Part A and Part B, in case a subject with a confirmed CR relapses after stopping treatment, but prior to the end of the trial, 1 re-initiation of treatment is allowed at the discretion of the Investigator and agreement of the trial Medical Monitor. In order to be eligible for retreatment, the subject must not have experienced any toxicity that led to treatment discontinuation of the initial avelumab therapy. Subjects who re-initiate treatment will stay on study and will be treated and monitored according to the protocol and the “until progression” schedule in the Schedule of Assessments (see Appendix I).

Assessments will be made by the Investigators for the purpose of subject management, but the primary and secondary endpoint determinations will be supported by tumor assessments performed by an IERC (see Sections 2.3.2 and 7.3).

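### Protocol 5.5.1 joins its conditions for continuing treatment beyond progression with *or* where *and* is needed, so sustained ECOG PS 3 or more can pass as no significant clinical deterioration

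*Protocol*

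**What the plan says.** Protocol Section 5.5.1 allows avelumab to continue past radiological progression when there is no significant clinical deterioration and "if in the opinion of the Investigator, the subject will benefit from continued treatment". It then lists what the absence of deterioration means, in three items:

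- The first is that no symptom is new or has become worse.
- The second, which carries the connective, reads "there is no change in ECOG PS to ≥ 3 that lasts more than 14 days, or".
- The third is that salvage therapy is not thought necessary by the Investigator.

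Later in the same section, continuation after local treatment of brain metastases is allowed "provided the above criteria are met in addition to the following and in consultation with the Medical Monitor".

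The protocol synopsis defines deterioration positively, by two elements joined by *and/or*. The first is "new symptoms or worsening of symptoms that cannot be managed by optimal supportive care or disease localization that require immediate medical or surgical intervention". The second is a change in ECOG PS to 3 or more lasting more than 14 days. Section 6 of the Part A SAP and Section 6 of the Part B SAP carry the same two-element definition.

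The protocol body refers to Section 5.5.1 for this rule. Section 5.1.1 permits treatment beyond progression "provided there is no significant clinical deterioration, see Section 5.5.1". Sections 5.5.3 and 7.1.2 also cite 5.5.1 for therapeutic failure.

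**The concern.** Three negated conditions that must all be satisfied have to be joined by *and*. Joined by *or*, the list is met as soon as one condition holds. A subject who has declined to sustained ECOG PS 3 or more would still qualify to continue if, for example, the Investigator saw no need for salvage therapy.

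This is a stopping rule in an open-label trial that expressly allows treatment beyond progression, at approximately 60 sites. An investigator should not have to work out from other sections that the stated logic is not the intended one. What is at stake is whether particular subjects stay on drug, and whether their continuation is recorded as a deviation.

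**Working it through.** No sample size, power or error rate is involved, so the check is one of wording and logic.

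**1. What the list defines.** Each item is worded as an absence. Read as a definition of deterioration itself, the list would make being free of symptoms a sign of deterioration, which is absurd. It must therefore define the absence of deterioration.

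**2. The correct negation.** In the synopsis, deterioration = A or B, where A is the symptom/localization element and B is sustained ECOG PS 3 or more. Hence no deterioration = (not A) *and* (not B). Section 5.5.1 writes the negated items but keeps the *or*.

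**3. Enumeration.** Let S = no new or worse symptoms, E = no sustained ECOG PS 3 or more, T = no salvage therapy needed. The columns show whether the subject counts as not deteriorated.

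| S | E | T | Literal *or* | With *and* |
|---|---|---|---|---|
| yes | yes | yes | yes | yes |
| yes | yes | no | yes | no |
| yes | no | yes | yes | no |
| yes | no | no | yes | no |
| no | yes | yes | yes | no |
| no | yes | no | yes | no |
| no | no | yes | yes | no |
| no | no | no | no | no |

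Literal *or* gives 7 of 8 rows as not deteriorated, and 3 of the 4 rows with sustained ECOG PS 3 or more. *And* gives 1 of 8 and 0 of 4. Under the synopsis and both SAP summaries the second figure is also 0 of 4, because element B suffices alone. The row that matters most in practice is the seventh: worse symptoms, sustained ECOG PS 3 or more, and no salvage therapy thought necessary. Literally, that subject is not deteriorated.

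**4. Evidence of intent.** The synopsis and both SAP summaries agree with each other. The brain-metastasis paragraph of 5.5.1 speaks of the criteria being met, in the plural. PDEV13 (Part A SAP Appendix II, Part B SAP Appendix I) lists continuing with unresolved ECOG PS 3 or more as a deviation. All point to *and*.

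**5. Differences that remain after changing the connective.** Section 5.5.1 has no supportive-care qualifier on symptoms, no disease-localization element, and an added salvage-therapy condition. Take the fifth row, with a new symptom that supportive care controls, ECOG PS below 3 and no salvage need. With *and* alone, 5.5.1 calls this deterioration; the synopsis elements do not. Changing one word would therefore introduce a different mismatch.

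**6. Reach of the term.** The synopsis dates progression and response duration from the first IERC-determined progression even when treatment continues. Part B SAP Section 16.2.2 does not treat clinical deterioration as documented progression. Neither per-protocol definition (Section 10 of each SAP) uses the term. PDEV13's first sentence uses it; its second sentence states the ECOG criterion directly and does not depend on the 5.5.1 list.

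**The case against.** The strongest reply is that nobody would apply the literal reading. The Investigator must expect benefit. Section 5.5.1 calls for discussion with the Medical Monitor and for an immediate stop when therapeutic failure leads to clinical progression or deterioration. Section 5.1.4.2 withholds the infusion if ECOG PS is 3 or more on the dosing day. PDEV13 would flag sustained ECOG PS 3 or more in any case. Two of the three problem rows pair sustained ECOG PS 3 or more with no new or worse symptoms, which is hardly realistic given the description of that grade in Appendix II.

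Much of this stands and keeps the point minor. It does not remove the error. The hold in Section 5.1.4.2 withholds a dose; it is not a withdrawal rule, and it sits in a list of exceptions to discontinuation for Grade 3 adverse drug reactions. The immediate-stop sentence uses its deterioration term without defining it, next to a definition whose logic is wrong. A deviation code applies after the fact.

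A second reply is that the synopsis also ends treatment when "any criterion for withdrawal from the trial or the study drug is fulfilled", so 5.5.1 always governs and the two texts can never give different stopping outcomes. That is circular: it brings 5.5.1 into the synopsis and then reports agreement. The definitions themselves differ, as step 5 of the working shows.

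**Conclusion.** The connective in Section 5.5.1 is wrong as written and contradicts the synopsis and both SAP summaries on sustained ECOG PS 3 or more. Severity is minor. The consequence is confined to decisions on continuing treatment and to the first sentence of PDEV13.

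Three stronger readings are tempting but unsupported:

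- **That efficacy results are compromised.** The definitions of the primary endpoints, progression dates and per-protocol sets do not use the term.
- **That the row counts measure the size of the problem.** They are unweighted logical combinations and change with how states are divided: splitting symptoms into three levels gives 10 of 12 and 4 of 6 in place of 7 of 8 and 3 of 4. The documents do not say how many subjects fall in any state, or that anyone was continued on the literal reading.
- **That 5.5.1, once corrected to *and*, should become the single definition everywhere.** That would drop the supportive-care qualifier and the localization element, which the synopsis and both SAPs share. It is a contestable clinical choice, not a correction.

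The conclusion assumes only that the synopsis and SAP wording reflects the sponsor's intent on ECOG PS, which PDEV13 supports.

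**What to change.** In Protocol Section 5.5.1, change *or* to *and*, and state that all conditions must hold for treatment to continue beyond progression. In the same edit, replace the unqualified symptom condition with the negation of the synopsis element: no symptoms beyond the control of optimal supportive care, and no disease site needing immediate medical or surgical intervention. Leave the ECOG condition as it is. The sponsor should decide whether to keep the salvage-therapy condition, which the synopsis and SAP summaries lack.

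The cost is a wording change in one protocol section. No new data are needed and no analysis changes. The SAP summaries already carry the intended two-element definition and can stay as they are.
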